### Study flow and Schedule of Events

Study personnel will explain the research risks and benefits. Written informed consent will be obtained for each study subject. The baseline diagnostic assessment, triage, treatment group assignment and follow up assessments are summarized in Fig. 1 and described in more detail in Specific Aim 2. Information regarding severity of alcohol withdrawal symptoms (measured by CIWA scale or site specific equivalent method) and medications used during withdrawal treatment preceding enrollment in the study will be collected or abstracted from the medical record and included in the data analyses.

\*Notation dated 5-12-2023: Upon IRB approval, subjects will no longer be randomized to the placebo arm. Instead, for the remainder of the study, all patients will be provided acamprosate to achieve the active drug and placebo ratio of 2:1.

Figure 1: Study Flow Chart

The presence of AUD and other psychiatric disorders will be confirmed by a computer version of the Psychiatric Research Interview for Substance and Mental Disorders (PRISM) [24]. The presence of comorbid depressive disorders requiring treatment will be determined by the combination of 2 characteristics: (1) the presence of any

diagnosis of depression during the previous year as confirmed by PRISM and verified by the study psychiatrist; and (2) a PHQ-9 score of 10 or above and/or a GAD-7 score of 10 or above. The interview will be conducted by interviewers trained and certified on the use of the PRISM. Interviewers, who have submitted required recordings and documents for certification and an unexpected delay in the certification process occurs, will be allowed to conduct prism assessment, if no other certified staff are available, with certification pending. The research pharmacy contracted for this study will randomize the study participants for all sites with placebo or acamprosate.

The schedule of study procedures and assessments is tabulated by visit in the Study Assessments in Table 1 (below). A visit window of +/- 10 days is allowed when scheduling. Questionnaires may be distributed in multiple formats (paper, electronic/mailed link, or asked/read to patient).

**Table 1: Study Assessments**

Study Assessments	Baseline Evaluation	Follow-Up Visits					
		2 week – TC	1 month #	6 week – TC	2 month #	10 week – TC	3 month #
Blood Collection	X		X				X
Medication provided	X		X		X		
PRISM	X						
LTDH	X						
CIWA-Ar	X						
TLFB ♦ (BDQ)	X		X		X		X
PHQ-9	X	X	X	X	X	X	X
GAD7	X	X	X	X	X	X	X
AAM			X		X		X
IDTS	X						
PACS	X		X				X
PRISE	X		X		X		X
FIBSER			X		X		X
PSQI	X		X		X		X
FIRM	X						
CD-RISC	X						X
Med. Compliance			X		X		X
Med. Compliance Enhancement		X		X		X	
CTA	X						
GGT lab test	X		X				X
CTQ	X						
CGI			X**		X**		

**Definitions:** AAM: AA attendance monitoring. CIWA-R: Clinical Institute Withdrawal Assessment-Research. CTA: Commitment to Abstinence. CTQ: Childhood Trauma Questionnaire. FIBSER: Frequency, Intensity and Burden of Side Effects Ratings. GGT: gamma-glutamyl transpeptidase lab test. IDTS: Inventory of Drug Taking Situations. LTDH: Lifetime Drinking History. PACS: Penn Alcohol Craving Scale. PHQ-9: Patient Health Questionnaire 9-item. GAD7: Generalized Anxiety Disorder 7-item. PRISE: Patient-rated Inventory of Side Effects. PRISM: Psychiatric Research Interview for Substance and Mental Disorders. TC: Telephone Call TLFB: The Alcohol Timeline Follow Back. PSQI: Pittsburgh Sleep Quality Index. FIRM: Family Index of Risk for Mood. CD-RISC: Connor-Davidson Resilience Scale (CD-RISC); CGI: Clinical Global Impression (CGI); \*\*Used by study psychiatrist to assess worsening mood symptoms despite antidepressant treatment during study participation. ♦ Brief Drinking Questionnaire (BDQ). # Allow the use of alternative formats to face-to-face visits based on concern for COVID exposure or other circumstances potentially preventing patients from attending face-to-face visits (blood draw done in person).

### Description of Assessment Instruments:

**PRISM:** Psychiatric Research Interview for Substance and Mental Disorders (PRISM) will be used for standardized assessment of Substance Use Disorders and comorbid conditions. PRISM is an electronic computer-based tool providing systematic coverage of the longitudinal course of alcohol- and drug-related experiences and psychiatric symptoms that may be useful in identifying areas of focus for treatment. The PRISM follows a decision-tree format using diagnostic algorithms for all Axis 1 psychiatric disorders plus Borderline and Antisocial Personality Disorders. Acceptable reliability and diagnostic validity of PRISM has been demonstrated [25, 26].

**LTDH:** The Lifetime Drinking History questionnaire (LTDH) provides a self-report of patterns of alcohol consumption over a person's lifetime [27]. A modified version allowing for the assessment of initial tolerance and maximum alcohol consumption in a 24-hour period will be used to provide the clinical projects with a description of the study samples and to investigate the potential impact of the LTDH on the primary and secondary treatment outcomes.

**CIWA-Ar:** The revised Clinical Institute Withdrawal Assessment for Alcohol (CIWA-Ar) scale. This assessment for monitoring withdrawal symptoms requires approximately 5 minutes to administer. The maximum score is 67. Patients scoring less than 10 do not usually need additional medication for withdrawal [28].

**TLFB:** The Alcohol Timeline Follow Back (TLFB) is a drinking assessment method that obtains estimates of daily drinking and has been evaluated with clinical and nonclinical populations. Using a calendar, people provide retrospective estimates of their daily drinking over a specified time period that can vary up to 12 months from the interview date[29].

**PHQ-9:** The 9-Item Patient Health Questionnaire (PHQ-9). The PHQ-9 consists of nine questions, rated 0–3 according to the increased frequency of difficulty experienced in each area covered. Scores, with a possible range of 0–27, are summed and can then be interpreted as follows: no depression (0), minimal (1–5), mild (6–9), moderate (10–14), moderately severe (15–19), or severe (>20) depression.

**GAD-7:** Generalized Anxiety Disorder 7 (GAD-7) is a self-reported questionnaire for screening and severity measuring of generalized anxiety disorder (GAD). GAD-7 has seven items, which measure severity of various signs of GAD according to reported response categories with assigned points. This will take approximately 5 minutes to complete.

**AA Monitoring:** Self-monitoring of attendance of Alcoholics Anonymous meetings (AAM) and sponsorship [30] will be used as a potential covariate and predictor of treatment response.

Evidence supports the importance of motivation for sobriety and attendance of support groups for treatment outcomes in alcoholics [31, 32]. Therefore, we will collect CTA and AAM data to allow for the assessment of the impact of these factors on treatment outcomes.

**IDTS:** The Inventory of Drug-Taking Situations (IDTS), developed by Annis and Martin (1985) [33], is a 50-item self-report questionnaire that provides a profile of the situations in which a client has used alcohol or another drug over the past year. Clients are asked to indicate their frequency of heavy drinking or drug use in each of 50 situations on a 4-point scale ranging from "never" to "almost always." The questionnaire may be administered in either pencil-and-paper or computerized version; the latter allows a client to name up to three substances that are currently causing a problem; the 50 IDTS items are presented for each substance in turn, and a computer-generated report is produced for each substance.

**PACS:** The Penn Alcohol Craving Scale (PACS) is a five-item self-administered instrument for assessing frequency, intensity, and duration of craving [34, 35]. The questions on the PACS use descriptors coupled with numerical ratings ranging from 0 to 6. PACS will be used to assess intensity of craving at baseline and follow up visits as a potential predictor of treatment response.

Intensity of craving and its contextual meaning (e.g. negative or relief craving) were associated with abstinence from alcohol and acamprosate response [36-38]. Therefore, we will collect PACS and IDTS data to allow for assessment of the impact of these factors on treatment outcomes.

**PRISE:** Patient-Rated Inventory of Side Effects (PRISE) is a self-report form used to qualify adverse effects as tolerable or distressing in 9 different domains, each with multiple symptoms [39].

**FIBSER:** Frequency, Intensity and Burden of Side Effects Ratings (FIBSER) is a self-report form used to quantify the adverse effect burden [40].

**CTA:** Commitment to Abstinence (CTA) will be determined by the subject's response to a questionnaire developed by Hall and colleagues in 1990 and modified with permission [41].

**CTQ:** The Childhood Trauma Questionnaire (CTQ) was developed as screening tools for histories of abuse and neglect. The self-report includes a 28-item test that measures 5 types of maltreatment – emotional, physical, and sexual abuse, and emotional and physical neglect. Approximately 5 minutes is required to complete the test. A 5-point Likert scale is used for the responses which range from Never True to Very Often True.

**FIRM:** Family Index of Risk for Mood (FIRM) is a self-reported tool developed to gather family history of psychiatric and seizure illness. The FIRM has demonstrated clinical significance in detecting pediatric bipolar disorder. [44]

**CD-RISC:** Connor-Davidson Resilience Scale (CD-RISC) is a self-rating scale to assess resilience. Resilience may be viewed as a measure of stress coping ability and, as such, could be an important target of treatment in anxiety, depression, and stress reactions. The CD-RISC has sound psychometric properties and distinguishes between those with greater and lesser resilience. [45]

**CGI:** Clinical Global Impression (CGI) is an assessment used by study psychiatrist for clinical judgment of depression symptoms' severity and worsening symptoms during the course of study participation. [46]

**Side Effects Assessment:** Assessment of side effects is critical to ensure safety of study participants and for the assessment of tolerability of the treatments. Therefore, we will collect PRISE and FIBSER data to monitor study participants for safety during treatment with study medications and to allow for the assessment of the impact of these factors on treatment outcomes.

**PSQI:** Pittsburgh Sleep Quality Index is a self-rated questionnaire which assesses sleep quality and disturbances over a 1-month time interval. Nineteen individual items generate seven “component” scores including: subjective sleep quality, sleep latency, sleep duration, habitual sleep efficiency, sleep disturbances, use of sleeping medication, and daytime dysfunction.

**BDQ:** Brief Drinking Questionnaire is used as an alternative to collecting drinking information if a patient refuses to complete the TLFB assessment. Six questions are asked to assess relapsed drinking during a period of time (i.e. between follow-up visits).

#### ***Remuneration:***

All participants will be paid \$40 each for completing Baseline, Month 1 and Month 2 visits and paid \$50 for completing the Month 3 visit for a total of \$170. Non-Mayo patients will be given a Visa gift card for the appropriate dollar amount corresponding to completed visits. Mileage reimbursement will be available for travel costs up to the amount of \$75 per visit.

### ***Study Medications:***

All participants will be randomized to receive acamprosate or placebo\* in a double-blinded placebo-controlled trial. Acamprosate, SSRIs, and SNRIs listed are FDA approved medications for the indications for which they are being used in this protocol; therefore the risk to participants is no more than that to the general population who may be taking these medications. Medication/Placebo\* administration starts with 1 pill 3 times a day for 7 days then increases to 2 pills 3 times a day.

\*Notation dated 5-12-2023: Upon IRB approval, subjects will no longer be randomized to the placebo arm. Instead, for the remainder of the study, all patients will be provided acamprosate to achieve the active drug and placebo ratio of 2:1.

***Potential Side Effects:*** Participants could be at risk of the potential side effects of one or both of these medications, which they will be made aware of at the time of obtaining informed consent and will be monitored on a monthly basis. Acamprosate is reasonably well tolerated in most patients. The most common side effect associated with acamprosate use is diarrhea, which occurs in approximately 16% of patients. Other frequently occurring side effects include asthenia, nausea, pruritus, and flatulence, headache, abdominal pain, flu syndrome, edema, weight gain, and myalgia. Infrequent side effects include ascites, face edema, photosensitivity reaction, suicidal ideation, suicide attempts, completed suicide, and acute kidney failure. The potential serious side effects of acamprosate are rare and include cardiomyopathy, deep vein thrombophlebitis, heart failure, and mesenteric arterial occlusion. The common side effects of SSRIs, and SNRIs listed on table 3 (page 14) are, but not limited to, diaphoresis, abdominal pain, constipation, diarrhea, indigestion, nausea, vomiting, xerostomia, dizziness, headache, insomnia, somnolence, disorder of ejaculation, impotence, orgasm incapacity, reduced libido, and fatigue. The potential serious side effects of are worsening depression, suicidal thoughts, and serotonin syndrome. It is possible that the intensity of depressive or anxiety symptoms may increase despite treatment and patients may develop suicidal ideation. It is also possible that patients may become medically unstable due to conditions unrelated to study treatment. The study team will meet regularly to review any side effects or adverse events reported and modify the protocol accordingly. Study participants developing side effects requiring medical attention will be referred to appropriate medical facilities.

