### ***Study Assessments and Procedures***

#### **Assessments**

A standardized clinical assessment is performed for all patients admitted to above mentioned treatment programs. This assessment will be used by study personnel to determine study eligibility, and determine if there is a need to discuss treatment of depression and/or anxiety. The Study Psychiatrist affiliated with each study site, or a member of the clinical treating team will meet with the patient to assess appropriateness and discuss potential benefits and risks associated. For patients meeting study inclusion and exclusion criteria and signing Informed Consent, the presence of AUD and comorbid conditions including depressive and anxiety disorders will be confirmed by Psychiatric Research Interview for Substance and Mental disorders (PRISM). The severity of depression and anxiety symptoms will be assessed by the Patient Health Questionnaire (PHQ-9) and Generalized Anxiety Disorder (GAD-7), respectively. In addition, alcohol use history, alcohol craving intensity, LFT levels and other relevant measures will be assessed at baseline and repeated at follow up visits as defined in Table 1.

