- (1) We will standardize depression and anxiety treatment by accepting current and stable use of SSRI & SNRI medications listed in table 3 (page 14) in all participants with depression and/or anxiety diagnoses. This will allow for an assessment of the impact of depression and/or anxiety as well as their standardized treatment on acamprosate and placebo-related treatment outcomes and account for this impact in genetic and metabolomic association analyses. Patients with newly diagnosed anxiety or depression as well as patients with known diagnosis but not taking any antidepressant will be offered treatment with escitalopram or citalopram as first line treatment during study participation when their GAD-7 or PHQ-9 scores are equal or above 10. We selected escitalopram based on evidence suggesting it is strongest among selective serotonin reuptake inhibitors (SSRIs) [18] and favoring it over other antidepressants in terms of efficacy and tolerability [19]. Clinical findings in adults with AUD and depression as well as our experimental data also suggest that the combined use of escitalopram and acamprosate may improve treatment outcomes [20, 21]. This threshold has been chosen based on previous research showing that PHQ-9 score  $\geq 10$ , indicative of the presence of at least moderate depression and/or a GAD-7 score of  $\geq 10$ , indicative of the presence of at least moderate anxiety reflect a clinically significant level of symptom severity warranting the use of medications [16, 17]. Results of treatment with escitalopram or citalopram will be monitored by the study

psychiatrist affiliated with each study site who will make appropriate treatment recommendations as described below.

[figure not shown]
(2) To avoid the impact of end stage liver disease on clinical and metabolomic findings, we will use a Model for End-Stage Liver Disease (MELD) score of 10 and below as a cut off for *inclusion* in the study, and will *exclude* patients with a diagnosis of advanced liver disease or those with a MELD score above 10, which is considered an indication that the extent of liver damage has reached an advanced stage [22, 23]. The MELD score will be calculated according to the standard approach using serum concentrations of bilirubin and creatinine, and the international normalized ratio for prothrombin time [22].

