### ***In-study risks and safety procedures:***

**General considerations:** Participant's treatment response as well as frequency and intensity of adverse effects will be discussed at baseline and assessed during follow-up visits with study staff. The study blind will be removed if any Unanticipated Problems Involving Risk To Subjects or Others (UPIRTSO) or adverse events is determined to be potentially related to the study medication (as deemed by treating study psychiatrist and study PI). Should concerns emerge regarding the patient's clinical problems not related to this study, those should be addressed by primary care specialist of patient's choice. If deemed necessary by study personnel, an urgent discussion with a study psychiatrist will take place for evaluation, and appropriate referral for treatment will be made. Study consent form includes participant's consent for permission to interface with his/her primary provider should clinical concerns arise.

**Depression Safety Management Plan:** The study team members will not be providing clinical care for conditions other than treatment of AUD and comorbid depression or anxiety. Therefore, any findings from PRISM assessment raising safety concerns, including positive response to suicide questions will trigger immediate notification to study psychiatrist and patient's clinician. In addition, if a subject endorses suicidality with any of the following: Active suicidal ideation as determined by the investigator or as determined by PHQ-9 (Question 9 score of 1 or higher) or if a subject responds positively to questions regarding the harm of self and/or others, the research team will immediately contact the study psychiatrist to refer for appropriate treatment.

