#### Exclusion Criteria:

1. Hypersensitivity or allergy to acamprosate
2. Current use of wellbutrin and not willing to switch to an acceptable antidepressant medication
3. Renal impairment (creatinine level >1.5 mg/dL);
4. Diagnosis of advanced liver disease indicated in the medical record or by a MELD score of above 10;
5. Women who are pregnant, breastfeeding, or planning to become pregnant during the next year;
6. Primary diagnosis of substance use disorder other than alcohol as determined by PRISM or in medical record review or secondary diagnosis of active (within the past year) benzo/sedative dependence, opioid dependence, stimulant dependence, heroin dependence, and/or cocaine dependence
7. Refusal to abstain from any chronic/daily use of prescribed benzodiazepines, opioids, stimulants, cannabis related medication such as CBD or medical marijuana, during the course of participation.
8. Current use of Naltrexone and not willing to stop and switch to Acamprosate/Placebo\* (see notation dated 5-12-2023 above)
9. Current use of Antabuse.

10. Active suicidal ideation or any unstable medical or psychiatric condition as determined by responses to PRISM or by the investigator.
11. Status of involuntary or court-ordered admission at time of consent.

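### Optional safety improvement: the protocol lists acute kidney failure as an acamprosate side effect but specifies no renal test after entry, and creatinine could be run on the serum tube already drawn at month 1

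*Combined protocol and SAP*

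**What the plan says.** All places are in the combined protocol and SAP.

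- **Named harm.** Study Medications, Potential Side Effects: "Infrequent side effects include ascites, face edema, photosensitivity reaction, suicidal ideation, suicide attempts, completed suicide, and acute kidney failure".
- **Entry screen.** Exclusion criterion 3 is "Renal impairment (creatinine level >1.5 mg/dL"). Creatinine is used once more at entry, for the liver-disease cut-off: "The MELD score will be calculated according to the standard approach using serum concentrations of bilirubin and creatinine", together with the INR.
- **Repeat measures.** The Assessments section states: "LFT levels and other relevant measures will be assessed at baseline and repeated at follow up visits as defined in Table 1". The only laboratory test named in Table 1 is GGT, at baseline, month 1 and month 3.
- **Blood.** The Biospecimens section gives three draws (baseline, months 1 and 3). The listed uses are GGT on a serum separator tube, DNA, acamprosate levels, metabolomics, proteomics and mRNA. A Table 1 footnote keeps the blood draw in person even when the rest of a visit is not.
- **Drug supply and contact.** Table 1 provides medication at baseline, month 1 and month 2. Its row "Med. Compliance Enhancement" is marked at the week 2, 6 and 10 calls.
- **Safety capture.** PRISE and FIBSER, both self-report, are completed at months 1, 2 and 3. In addition, "frequency and intensity of adverse effects will be discussed at baseline and assessed during follow-up visits with study staff". Action is by referral: "Study participants developing side effects requiring medical attention will be referred to appropriate medical facilities".

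**The concern.** The protocol treats the kidney as relevant to this drug in two ways: it names a serious renal side effect, and it uses a laboratory value, not symptoms, to decide who is too impaired to receive the drug. After entry that laboratory value disappears from the plan. Two further supplies and three compliance calls go ahead with no renal result specified to inform them.

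Suicidal ideation, listed in the same sentence as acute kidney failure, is handled differently. It has a scheduled measure (PHQ-9 at all seven contacts in Table 1), a trigger (question 9 scored 1 or higher) and an escalation path. Acute kidney failure has only the general side-effect route.

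What is at stake is narrow. Injury that causes symptoms could surface through the questionnaires or staff review. A rise without symptoms has no specified route to detection. The matter concerns participant safety and does not touch the primary endpoint or the genetic analyses.

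**Working it through.** The plan states no figure to reproduce. The check is a search of the text for renal tests, a count from Table 1, and arithmetic on timing and on the trigger.

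**1. Where a renal test is named**

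| Place | Renal test? |
|---|---|
| Exclusion criterion 3 | Creatinine, at entry |
| MELD score | Creatinine, at entry |
| Table 1 | None |
| Biospecimens tube list | None |
| Potential Side Effects; In-study risks and safety procedures | None |
| Analysis for Specific Aim 2a | None (liver tests only, as covariates) |

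Acamprosate blood levels are assayed alongside the metabolomic samples. No safety limit or prompt review is stated for them, so they do not stand in for creatinine.

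**2. Counts from Table 1**

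- Supplies: baseline, month 1, month 2 = 3, of which 3 − 1 = 2 follow entry.
- Draws: baseline, month 1, month 3 = 3, of which 3 − 1 = 2 follow entry.
- Follow-up draws that precede a later supply: 1 (month 1, before month 2). Month 3 comes after the last supply.
- Renal tests specified after entry: 0.

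**3. Is month 1 early enough?** Assume 30-day months. The protocol adds: "A visit window of +/- 10 days is allowed when scheduling".

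- Nominal gap from month 1 draw to month 2 supply: 60 − 30 = 30 days.
- Shortest: (60 − 10) − (30 + 10) = 10 days.
- Longest: (60 + 10) − (30 − 10) = 50 days.
- Week 6 call: 6 × 7 = day 42, so 42 − 30 = 12 days after a day 30 draw. If the window also applies to calls, the earliest call against the latest draw gives (42 − 10) − (30 + 10) = −8 days, so the call could precede the draw. The dependable review point is the month 2 supply.

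The month 1 supply is given at the same visit as the draw, so the result would not normally inform that supply.

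**4. Which trigger?** Compare an absolute limit of 1.5 mg/dL with a limit of 1.5 times the entry value (an assumed example).

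- Entry 0.7, month 1 value 1.4: ratio 1.4 / 0.7 = 2.0. The absolute limit misses this doubling. The ratio rule flags it, since 0.7 × 1.5 = 1.05.
- Entry 1.5 (still eligible), month 1 value 1.6: ratio 1.6 / 1.5 = 1.07. The absolute limit flags this small drift. The ratio rule does not, since 1.5 × 1.5 = 2.25.
- The ratio limit exceeds 1.5 mg/dL whenever the entry value exceeds 1.5 / 1.5 = 1.0 mg/dL. For those participants a second condition is useful: above 1.5 mg/dL and meaningfully higher than at entry.

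**5. Number who would benefit.** This cannot be computed. The documents give neither a rate for renal events nor the number of participants still to reach month 1.

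**The case against.** The strongest case for leaving the plan alone has five parts.

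- **No rule is broken.** The 1.5 mg/dL limit is stated only for entry. This stands.
- **Ordinary risk.** Study Medications argues that these are approved drugs used for approved indications, so participants run no more risk than other people taking them. That is a fair answer to any claim that the trial is unsafe, and showing that ordinary use calls for repeat creatinine would need sources outside the documents. It does not remove the low-burden case for one check.
- **Weak inference from absence.** Table 1 and the tube list also leave out entry creatinine, bilirubin and INR, and the AST and ALT used as baseline covariates. They are not a full list of clinical laboratory work. A reader might infer that kidney function is not followed at all; the documents do not support that. They show only that no repeat is specified.
- **Benefit and cost are both unquantified.** This stands. Assay cost, tube volume and turnaround are not stated, so calling the test cheap is a judgement. The text supports only that no new visit or venipuncture is needed.
- **Limited reach.** One value misses later rises, and the notation dated 5-12-2023 shows the trial was already under way. This also stands.

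Existing safeguards (questionnaires, staff review, urgent discussion with a psychiatrist, referral, regular team review of side effects) cover symptomatic injury. What remains is a symptom-free rise of unknown frequency and consequence.

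**Conclusion.** The gap is real but small. Followed as written, the plan names acute kidney failure, checks creatinine at entry and then resupplies drug twice with 0 renal tests specified. Under that schedule a symptom-free rise could go unnoticed. One existing draw, at month 1, falls before a later supply, by about 30 days (10 to 50 with the visit windows, assuming 30-day months).

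This is an optional improvement to a design choice, justified by low burden and not by a demonstrated benefit. A reader might go further and infer a breach of the protocol's own renal limit, an unsafe trial or a threat to the results. None of these follows: the limit governs entry only, no event rate is given, and no analysis or conclusion of the trial changes. The conclusion rests on the schedule as written; if sites already repeat creatinine clinically, the gap is one of documentation.

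**What to change.** For participants still to reach month 1:

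1. Run serum creatinine on the serum separator tube already drawn for GGT at month 1. Add it to Table 1 and to the Biospecimens tube list. Where a site already repeats creatinine in usual care, use that result and say so.
2. Review the result before the month 2 supply.
3. In the In-study risks and safety procedures section, state that the site's study psychiatrist is told of either (a) a clear rise from the participant's own entry value, for example 1.5 times or more, or (b) a value above 1.5 mg/dL that is also meaningfully higher than at entry. The 1.5-fold limit and the margin in (b) are for the sponsor to set.
4. Limit the psychiatrist's role to holding study drug and referring to the primary provider, for which the consent form already gives permission. This respects the study team's stated scope of care.

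**Costs.** A small assay cost; prompt reporting and review at each site; incidental abnormal values to handle; and tube volume and turnaround to confirm. Because the blind is removed when an adverse event is judged potentially drug related, some results could add unblinding. That matters little for participants enrolled after placebo assignment stopped, since all of them receive acamprosate. Rises after the month 1 draw would still be missed before the month 2 supply, because there is no month 2 draw.
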